8.13 Medical Care for Subjects Following the End of the Study

Subjects will sign a consent, which states that they will receive an economical compensation for their participation in the study. The Sponsor will pay treatment (or compensation, if applicable) resulting from injuries or diseases caused by their participation in the study until their resolution as per the clinical criteria. The Sponsor will not pay injuries caused by subject's negligence, irresponsible behavior or medical reasons no related to the study.

External follow-up will be given to all subjects recruited in the study. As per the last dose of the drug, free appointment or telephone contact will be available as per the Principal Investigator's judgment, for a period equivalent to the established wash-out period.

9 Study Assessments and Procedures

9.1.1 Subjects screening

Screening of the subjects will take place within 30 days prior to the first administration of the trial medication and comprises the following:

- Informed consent for participation in the trial,
- Inclusion/exclusion criteria checked.
- Demographics (including nicotine consumption, smoking history, alcohol consumption, intake of caffeine or xanthine-containing beverages, intake of grapefruit, orange, cranberry or juices of these three fruits and diet as described in Section 6.3.2)
- Medical history and history of medications
- Vital signs (body temperature [tympanic], as well as blood pressure (BP) and pulse rate after at least 5 minutes rest in supine position),
- Physical examination (including measurement of weight and height),
- Safety laboratory: biochemistry tests, hematological tests and urinalysis, coagulation and virology,
- A urine drug screen and alcohol breath test,
- Serum pregnancy test (WOCBP only),
- 12-lead standard ECG (after 5 minutes rest in supine position),

AEs, concomitant medications and procedures will be continuously assessed from signature of informed consent to the end-of-trial examination.

If no clinically relevant finding is made at screening and the subject satisfies all of the protocol inclusion criteria and none of the exclusion criteria, he/she will be considered as eligible and will be enrolled into the clinical trial.

Subjects who fail to meet the protocol specified criteria for dosing or who withdraw their consent in the screening period are considered screening failures. The following data will be recorded for these subjects: demographics (including age, sex, weight and height), AEs, concomitant medications and reason for screening failure.

9.1.2 Study periods

At the beginning of each period, a clinical assessment consisting of an examination by apparatus and systems will be made in order to check if the subject remains eligible for the study. Blood will be taken for pregnancy tests for women of childbearing potential and urine samples for drug screening. Oral alcohol test will also be performed.

Subjects should inform the medical staff in charge of the study conduct about any symptom they might have. Likewise, medical staff will question the subjects in every study period about symptoms occurred since recruitment in the first period, prior and following dosing. In case they report any, they will be provided with care and notes will be made in the appropriate documents.

During admission, subjects will be continuously monitored and an electrocardiogram will be performed pre-dose, during each discharge (48 h post-dose) and during the last outpatient sampling (168 h post-dose) at each visit.

During each admission, blood and urine samples will be taken from subjects for safety laboratory tests such as hematology, blood chemistry, prothrombin time (PT) and partial thromboplastin time (PTT) and urinalysis. Samples will be taken pre-dose (following 10-h fasting) and at discharge (48 h post-dose).

Glucose measurements will be performed: at each pre-dose and 4, 12, 24, and 32 h post-dose. Finger stick glucose measurement (Hematoglucotest) will be made at each pre-dose and 2, 4, 8, 12 and 24 h post-dose.

At the end of each period and at the last outpatient sample (sample 168.00 h post-dose) a clinical assessment will be made. It will consist of an interview, physical examination (oral cavity examination, lungs, heart, abdomen and other organs, if necessary in case of symptoms), vital signs measurement and follow-up of adverse events. Blood and urine samples will be taken for safety laboratory tests such as hematology; blood chemistry, prothrombin time (PT) and partial thromboplastin time (PTT); and urinalysis.

At the last visit for outpatient sampling (168.00 h post-dose) a clinical assessment will be performed consisting of an interview, physical examination (oral cavity examination, lungs, heart, abdomen and other organs, if necessary in case of symptoms).

Weight and height, and vital signs will be measured; and electrocardiogram and adverse events follow-up will be carried out. Blood samples will be taken for pregnancy tests for women of childbearing potential.

For post-menopausal women (amenorrhoeic for at least one year), post-menopausal condition will be confirmed by means of follicle-stimulating hormone level during screening period only.

Due to operational issues, the Principal Investigator may modify start of the study (starting as per the dosing of study drug) for one hour, as long as there is no impact on the study results.

9.1.3 Control of Meals and Liquid Intake

During study conduct, subjects should fast for at least 10 hours before the dosing and at least for 4 hours following the dosing. Water is allowed *ad libitum*, except for the period between one hour prior to dosing and the first meal.

During confinement, meals will be served as shown below. Forty five minutes (45) will be allowed for having meals; water consumption will not be subject to this period.

Feeding time

MEALS	DAY 0, 14, 28 and 42	DAY 1, 15, 29 and 43
Breakfast	-----	As from 12:00 h
Lunch	-----	As from 16:00 h
Dinner	21:00 h	As from 21:00 h

Groups will be outdated by two 2 minutes between each (after dosing) for food delivery for the order and interval of drug administration. Food and Liquids that were not intake completely must be described as protocol deviation.

9.2 Schedule of Assessments

Prior any study assessment, the Principal Investigator or designated person will obtain written informed consent.

9.2.1 First period of treatment

Day- 1:

- ✚ Admission the day prior to the visit for assuring 10-h fasting period.
- ✚ Dinner at least 10 h before the dosing.
- ✚ Subject's eligibility will be checked again before catheter insertion and drug's dosing.
- ✚ Catheter insertion (by choice, only women).

Day 1:

- ✚ At 5:00 h, grooming and intake of 250 mL of water.
- ✚ Between 05:20 and 06:30 h, electrocardiogram will be performed.
- ✚ Post electrocardiogram the following activities will be done
 - Catheter insertion (control or "0" sampling).
 - vital signs will be measured
 - Safety laboratory tests.
 - Blood glucose determination
 - Finger stick glucose
 - Adverse events and previous medication
- ✚ Randomization for the first period of treatment only
- ✚ At 08:00 h, oral administration of test or reference drug with 250 mL of water at room temperature p.o., according to the standard operating procedure, code: PPD PREPARATION AND ADMINISTRATION OF DRUGS IN INTERCHANGEABILITY AND BIOCOMPARABILITY CLINICAL STUDIES.
- ✚ From 08:30 to 00:00 h, sampling as per the sampling schedule.
- ✚ At 8:00 h, 0.5 PK sampling
- ✚ At 9:00 h, 1 PK sampling
 - At 10:00 h, 2 PK sampling and Finger stick glucose
- ✚ At 11:00 h, 3 PK sampling

- ✚ At 12:00 h, 4 PK sampling and Finger stick glucose, Blood glucose determination and vital signs
- ✚ As from 12:00 h, breakfast.
- ✚ At 13:00 h, 5 PK sampling
- ✚ At 14:00 h, 6 PK sampling
- ✚ At 15:00 h, 7 PK sampling
- ✚ At 16:00 h, 8 PK sampling and Finger stick glucose and vital signs
- ✚ As from 16:00 h, lunch.
- ✚ At 18:00 h, 10 PK sampling
- ✚ At 20:00 h, 12 PK sampling and Finger stick glucose, Blood glucose determination and vital signs
- ✚ As from 21:00 h, dinner.

Day 2:

- ✚ At 00:00 h, 16 PK sampling
- ✚ At 8:00 h, 24.0-h PK sampling, Finger stick glucose, Blood glucose determination and vital signs.
- ✚ At 12:00 h, 28.0-h PK sampling.
- ✚ At 16:00 h, 32.0-h PK sampling, Blood glucose determination and vital signs.

Day 3:

- ✚ At 8:00 h, 48.0-h PK sampling, physical examination, vital signs, electrocardiogram and Safety laboratory
- ✚ Approximately at 10:00 h, temporary discharge from the clinical unit.

Day 4

- ✚ At 8:00 h, 72.0-h PK sampling.

Day 5

- ✚ At 8:00 h, 96.0-h PK sampling.

Day 6

✚ At 8:00 h, 120.0-h PK sampling.

Day 7

✚ At 8:00 h, 144.0-h PK sampling.

Day 8

✚ At 8:00 h, 168.0-h PK sampling.

✚ Approximately at 10:00 h, temporary discharge and free appointment.

9.2.2 Wash-out period

Wash-out period lasts for 14 days after administration in each period. It is intended to clear the prior dose before administering the next one and to fulfill with the NOM-177-SSA1-2013 criterion about having a period of at least 7 half-lives for the study drug.

9.2.3 Second period of treatment

Like the First period of treatment but after 14 days

9.2.4 Wash-out period

Wash-out period lasts for 14 days after administration in each period. It is intended to clear the prior dose before administering the next one and to fulfill with the NOM-177-SSA1-2013 criterion about having a period of at least 7 half-lives for the study drug.

9.2.5 Third period of treatment

Like the First period of treatment but after 28 days

9.2.6 Wash-out period

Wash-out period lasts for 14 days after administration in each period. It is intended to clear the prior dose before administering the next one and to fulfill with the NOM-177-SSA1-2013 criterion about having a period of at least 7 half-lives for the study drug.

9.2.7 Fourth period of treatment

Like the First period of treatment but after 42 days

9.2.8 End of Trial

- ✚ At 8:00 h, 168.0-h PK sampling.
- ✚ interview, physical examination (oral cavity examination, lungs, heart, abdomen and other organs, if necessary in case of symptoms),
- ✚ Vital signs measurement and follow-up of adverse events.
- ✚ Safety laboratory tests.
- ✚ Weight and height will be measured;
- ✚ Electrocardiogram.
- ✚ Blood samples will be taken for pregnancy tests for women of childbearing potential.

9.3 Baseline demographic and other characteristics

At screening, the following demographic data will be collected: date of birth, sex (gender), race, ethnicity

Specify any additional critical variables to be assessed such as:

- Information about previous and concomitant medications
- Medical history data
- Previous medication
- Weight, height and BMI
- Special diets
- For women, menstrual status, date of last menstrual period, and serum pregnancy test.
- Month prior to drug administration, nicotine consumption
- Smoking history
- Alcohol consumption
- Caffeine or xanthine consumption -containing beverages, intake of grapefruit, orange, cranberry or juices of these three fruits, intake of food containing xanthine and usual diet.
- Physical examination, and serum virology
- Safety laboratory
- ECG
- Vital signs

9.4 Safety Assessments

Clinical safety will be assessed by means of a complete physical examination (before the study and 48 and 168 h post-dose). On the other hand, throughout the study, subjects will be continuously monitored, including vital signs measurement (baseline and 4, 8, 12, 24, 32, 48 and 168 h post-dose) and an electrocardiogram will be performed (baseline, 48 and 168 h post-dose).

Safety by means of laboratory will be assessed by means of full laboratory tests (baseline and 48 h post-dose in every period). In blood analyses besides glucose (baseline, 4, 12, 24, and 32 post-dose), finger-stick glucose (Hematoglucotest) will be monitored (baseline, 2, 4, 8, 12 and 24 h post-dose).

Investigational drugs' safety profile will be assessed by means of the record, report and analysis of baseline medical conditions, including the use of drugs, smoking habits and alcohol use, adverse events, findings in the physical examination, including vital signs, drug abuse screening, pregnancy test and laboratory tests.

Comprehensive assessment for any apparent toxicity experience by any subject should be carried out since informed consent signature and throughout the study. The Principal Investigator will report any adverse event, observed by him/her or the assigned medical staff or reported by the subject (see section 9.5.1.2). Reporting period for adverse events is described in section 8.4.1.3.

9.4.1 Adverse Event

9.4.1.1 Adverse Event Definitions

Adverse Event

An adverse event is any untoward medical occurrence which may occur during drug's clinical research stage but which do not necessarily has a causal relation with the drug. Therefore, an adverse event can be any untoward sign and symptom (including any abnormal finding in the laboratory tests), or condition temporarily related to the use of the drug (investigational), whether related or not to that product.

Adverse events associated to the use of drugs in humans, related or not to the drug, include the following:

- ✚ Any adverse event occurring during the use of the drug in the professional practice.
- ✚ An adverse event, which occurs because of the abuse of drug products or substances.
- ✚ An adverse event, which occur following the stop of drug's intake.
- ✚ An adverse event where there is a reasonable possibility that the event occurred only as a consequence of the subject's participation in the study (e.g., adverse event or serious

adverse event due to the stop of anti-hypertensive drugs during wash-out phase) should be reported as an adverse event even though this is not related to the investigational product.

- ✚ Clinical onset on any failure of the expected pharmacological action.

In case the event meets the criteria for "serious" adverse event, it should be recorded and reported as that.

9.4.1.2 Adverse Event's Causality with the Investigational Product

Adverse events' causality with study drug is a clinical decision based on all available information at the moment of the adverse event onset.

Adverse reactions are classified according to the causality according to the following probabilistic categories:

A causality assessment would include:

- ✚ **Certain.** It consists of an event (clinical onset or an abnormal result of laboratory test) which occurs within a reasonable period of time following the drug's administration and which cannot be explained by the natural condition's evolution, by any concomitant pathology or by other drugs dosing. Response to drug's stop should be clearly evident.
- ✚ **Probable.** It consists of an event (clinical onset or an abnormal result of laboratory test) which follows a reasonable period of time following the drug's administration and which can hardly be related to the natural condition's evolution, concomitant pathologies or to other drugs dosing. A clinically reasonable response is obtained upon stop of other(s) drug(s).
- ✚ **Possible.** It consists of an event (clinical onset or an abnormal result of laboratory test) which follows a reasonable period of time following the drug's administration and which can hardly be related to the natural condition's evolution, concomitant pathologies or to other drugs dosing. There is no information available related to the suspect drug's dosing or this is not clear.
- ✚ **Suspect.** It consists of a an event (clinical onset or abnormal laboratory test) which follows a reasonable sequence of time following the drug's dosing which makes causality unlikely (but not impossible). It might be explained in a reasonable way since it is part of the natural evolution of the condition, or it is due to the presence of concomitant pathologies or other drugs dosing.
- ✚ **Conditional - Unclassifiable** It consists of an event (clinical onset or abnormal laboratory test result) which cannot be properly assessed since more data are required or because additional data are still being analyzed.

- ✚ **Not evaluable - Unclassifiable** It consists of a report which suggest that there is an adverse reaction which cannot be assessed since collected information is not enough or inconsistent. The report cannot be completed or checked.

Other factors to be considered for adverse event's causality assessment with the study drug are:

- ✚ Recovery or discontinuation, relapse or rechallenge: Subject's response following stopping the drug or subject's response following rechallenge should be considered based on the usual clinical course of the corresponding event.
- ✚ Response pattern known for this type of drug: Clinical/Pre-clinical
- ✚ Exposure to physical and/or mental stress: Exposure to stress may produce adverse changes in the receptor and provide a rationale and a better explanation for the event.
- ✚ Test drug's pharmacology and pharmacokinetics: Test drug's pharmacokinetic properties (absorption, distribution, metabolism and excretion) as well as the subject's individual pharmacodynamics should be considered.

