In accordance with ICH GCP, the Sponsor/designee will inform the Investigator of “findings that could adversely affect the safety of subjects, impact the conduct of the trial or alter the IEC’s/IRB’s approval/favorable opinion to continue the trial.” In particular and in line with respective regulations, the Sponsor/designee will inform the Investigator of AEs that are both serious and unexpected and are considered to be related to the administered product (“suspected unexpected serious adverse reactions” or SUSARs). The Investigator should place copies of Safety Reports in the Investigator Site File. National regulations with regard to Safety Report notifications to Investigators will be taken into account.

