9.10.3 Safety Analyses

All safety endpoints will be analyzed descriptively.

Vital signs measurements and ECG recordings will be individually listed by subject number, treatment and time point and flagged according to reference ranges. All variables will be presented by descriptive statistics by treatment and time point for the values obtained during the treatment periods and overall and by treatment sequence at screening and the end of study visit.

All hematology and biochemistry parameters, including hematoglucoest (HGT) results, will be listed and summarized using descriptive statistics on observed values by treatment and time point for the values obtained during the treatment periods and overall and by treatment sequence at screening and end of study visit. Urinalysis will be summarized in frequency tables.

In addition, shift tables for laboratory tests based on a classification of values as low, normal, or high with respect to the reference range could be summarized and presented by time point.

After coding of AEs according to the Medical Dictionary for Regulatory Activities (MedDRA) classification (current version) and assignment to a system organ class (SOC), all AEs recorded during the course of the trial will be listed by treatment and subject number and tabulated by MedDRA SOC and Preferred Term (PT).

The frequency of treatment-emergent AEs (TEAEs) will be summarized using the frequency of events and the number of subjects experiencing these events per treatment, PT, and SOC.

In addition, all TEAEs will be tabulated by intensity and relationship to drug per treatment.

An AE will be tabulated by intensity since the first investigational product administration of each period or if it occurred before administration and worsened during the period. The results will be presented as a frequency proportions or histograms.

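### The causality levels in Protocol 9.4.1.2 are defective as written: the response clause in Probable names the wrong drug, mixed-cause events first fit at an unlikely level, and no level records an unrelated event

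*Protocol*

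**What the plan says.** Protocol 9.4.1.2 calls causality a clinical decision and then gives six levels.

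- *Certain*: other explanations are excluded, and "Response to drug's stop should be clearly evident".
- *Probable*: the event "can hardly be related to the natural condition's evolution, concomitant pathologies or to other drugs dosing", and then "A clinically reasonable response is obtained upon stop of other(s) drug(s".
- *Possible*: the same clause on other causes as in *Probable*, followed by "There is no information available related to the suspect drug's dosing or this is not clear".
- *Suspect*: a time sequence that "makes causality unlikely (but not impossible", with a reasonable explanation in the underlying condition, another illness or other drugs.
- *Conditional* and *Not evaluable*: both unclassifiable, for data that are awaited, insufficient or inconsistent.

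The section ends with further factors to weigh. One of them is the subject's response after stopping, or being given again, the drug.

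The grade is used in two places. Protocol 9.10.3 says that "all TEAEs will be tabulated by intensity and relationship to drug per treatment". Protocol 9.4.1.11 has the sponsor inform the investigator of "AEs that are both serious and unexpected and are considered to be related to the administered product", that is, SUSARs. SAP section 18 refers clinical results to the clinical report and gives no causality definition or mapping.

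**The concern.** A causality scale should rank events by how well the study drug explains them, and every recorded event should have a place on it. This one falls short in three ways. One level is tied to withdrawal of the wrong drug. The middle of the scale has no place for the common case of two plausible causes. The bottom has no place for an event that the drug did not cause.

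Comparing safety and tolerability across the four treatments is a stated secondary endpoint (Protocol section 1; SAP 6.2), and the relationship table is part of that description. If assessors follow the text, drug-plausible events and unrelated events share one level. If they depart from it, each decides how to, and the table cannot be reproduced. The SUSAR judgement also needs a related or not-related answer, and the plan never says where on the scale that line falls.

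**Working it through.** No arithmetic applies, because the point turns on wording. The definitions side by side:

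| Level | Alternative causes | Further condition |
|---|---|---|
| Certain | excluded | response to stopping the study drug |
| Probable | hardly credible | response to stopping other drugs |
| Possible | hardly credible (same clause) | information on the suspect drug's dosing missing or unclear |
| Suspect | reasonable explanation available | causality unlikely |
| Conditional | not judged | more data awaited |
| Not evaluable | not judged | data insufficient or inconsistent |

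Count over the six levels: one uses withdrawal of the study drug, one uses withdrawal of other drugs, two share the same near-exclusion of alternatives, one admits alternatives, two are for inadequate data, and none means unrelated.

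**Step 1: the response clause in *Probable*.** *Certain*, one level above, looks at stopping the drug. The further factors in 9.4.1.2 do the same. Only *Probable* looks at other drugs. Improvement after another drug is stopped is evidence for that other drug. Protocol 8.5.1 also bars concomitant drugs except those given for adverse events, so there will often be no other drug to stop.

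**Step 2: *Possible* against *Probable*.** The clause on other causes is the same, so *Possible* is no more open to an alternative explanation than *Probable*. What separates them is missing or unclear information on dosing, yet 8.9 has dose, full intake and time checked and recorded. If dosing was meant to read withdrawal, the levels would differ in their withdrawal evidence, but the shared clause would still shut out alternatives.

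**Step 3: a mixed-cause event.** Take nausea a few hours after a metformin dose in a subject who also shows signs of an intercurrent stomach infection (an illustration). Protocol 3.1.8 lists nausea as very common with metformin, so the drug is a plausible cause. The infection is a concomitant illness that also explains the event.
- *Certain* fails, because the alternative is not excluded.
- *Probable* and *Possible* fail, because the event can readily be related to another illness.
- *Suspect* is the first level that admits the alternative, but it requires causality to be unlikely, which is not the judgement here.

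**Step 4: an unrelated event.** Take an accidental injury after dosing. Protocol 9.4.1.1 counts an untoward event as an adverse event whether or not it is related to the product, so it is recorded and enters the TEAE table. *Suspect* overstates the link, since it means unlikely but still possible. The two unclassifiable levels are for poor or pending information, which is not the problem here.

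**Step 5: use of the grade.** 9.10.3 applies the scale to all TEAEs and 9.4.1.11 uses the word related. Neither says which levels count as related, and the SAP does not supply the cut.

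**The case against.** The strongest reply is that little depends on the grade, and much of it stands.

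- **Reporting.** Protocol 9.4.1.10 sends any new SAE to the sponsor within 24 hours and any SAE to the national pharmacovigilance centre within 24 hours. Under 9.4.1.11 all serious and non-serious adverse events go to the committees and health authorities. None of this depends on the causality grade. A reader might infer that a serious event could go unseen because it was graded *Suspect*; these sections rule that out. What remains open is the relatedness judgement for a SUSAR.
- **Treatment comparison.** 9.10.3 summarises TEAE events and subjects by treatment, preferred term and system organ class without the scale. The relationship table is an additional descriptive output.
- **Attainability.** A reader might infer that *Certain* and *Probable* can never be reached after single doses. The documents do not show this. In the crossover of 7.1 each completing subject receives metformin in three of four periods and gliclazide in three of four, with 14-day wash-outs, so recovery and re-exposure can be observed. Recovery as the drug clears can be read as a response to stopping, and drugs given for adverse events are allowed.
- **Judgement.** 9.4.1.2 calls causality a clinical decision on all available information and lists further factors, so an assessor could work around the text. The clause shared by *Probable* and *Possible* is near-exclusion, not absolute exclusion. It is therefore too strong to say that events will be misclassified.
- **Unrelated events.** The levels are introduced as classifying adverse reactions, which might explain why none means unrelated. But 9.10.3 tabulates all TEAEs by relationship and does not say where unrelated ones go.
- **National rules.** The national pharmacovigilance standard and the site procedure are cited but not available here. The category names may be prescribed, so renaming them should not be assumed to be open.

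The general factors do not repair the level definitions. They show what *Probable* probably meant, and so confirm that the clause as printed is wrong.

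**Conclusion.** The point holds for the wording of 9.4.1.2. *Probable* names the wrong drug. An event with both a plausible drug cause and a plausible alternative first fits at a level defined as unlikely. Unrelated events have no level. Nothing elsewhere in the protocol or SAP corrects this.

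The consequence is limited. Under a literal reading, the descriptive TEAE-by-relationship table misplaces mixed-cause and unrelated events, and the SUSAR judgement has no stated cut. SAE reporting, overall TEAE frequencies by treatment, PK endpoints, sample size and error rates are unaffected.

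The documents give no expected event counts, so the number of misplaced events cannot be stated. A reader might multiply 40 subjects by 4 periods and call all 160 planned dosings affected, but that counts exposures, not events. The conclusion assumes that assessors apply the definitions as printed and that no mapping exists in the procedures not available here. The change is worth making because the table depends on it and the cost is small.

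**What to change.** In Protocol 9.4.1.2:

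1. Make the response clause in *Probable* refer to the study drug. For a single dose, word it as recovery consistent with elimination of that drug.
2. Reword *Possible* so that it admits a plausible alternative cause.
3. Add a *Not related* level.
4. State which levels count as related, and use the same cut for the 9.10.3 table and for SUSARs. Repeat it in the SAP.

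If the national form requires its own category names, including *Suspect*, keep them and map them to the corrected levels. If events have already been graded when the correction is made, the clinical report should state the mapping and identify any events that were re-graded.

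The cost is protocol wording, one CRF code list and the mapping to the national form. No visits, samples or subjects are added.
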